**Table 5.1-2: AE date imputation**

|                        | MON  | MON < CFM              | MON = CFM              | MON > CFM              |
|------------------------|--|------------------------|------------------------|------------------------|
|                        | MISSING  |                        |                        |                        |
| YYYY MISSING           | NULL   | NULL                   | NULL                   | NULL                   |
|                        | Uncertain  | Uncertain              | Uncertain              | Uncertain              |
| YYYY < CFY             | ( D ) = 01JULYYYY  | ( C ) = 15MONYYYY      | ( C ) = 15MONYYYY      | ( C ) = 15MONYYYY      |
|                        | Before Treatment Start   | Before Treatment Start | Before Treatment Start | Before Treatment Start |
| YYYY = CFY             | (B)= TRTSTD+1  | ( C ) = 15MONYYYY      | (A)= TRTSTD+1          | (A)= 01MONYYYY         |
|                        | Uncertain  | Before Treatment Start | Uncertain              | After Treatment Start  |
| YYYY > CFY             | (E)= 01JANYYYY   | (A)= 01MONYYYY         | (A)= 01MONYYYY         | (A)= 01MONYYYY         |
|                        | After Treatment Start  | After Treatment Start  | After Treatment Start  | After Treatment Start  |
| Before Treatment Start | Partial indicates date prior to Treatment Start Date                   |                        |                        |                        |
| After Treatment Start  | Partial indicates date after Treatment Start Date                      |                        |                        |                        |
| Uncertain              | Partial insufficient to determine relationship to Treatment Start Date |                        |                        |                        |
| LEGEND:         |  |                        |                        |                        |
| (A)                    | MAX(01MONYYYY,TRTSTD+1)  |                        |                        |                        |
| (B)                    | TRTSTD+1   |                        |                        |                        |
| (C)                    | 15MONYYYY  |                        |                        |                        |
| (D)                    | 01JULYYYY  |                        |                        |                        |
| (E)                    | 01JANYYYY  |                        |                        |                        |

### 5.1.3 Concomitant medication date imputation

Concomitant medication (CMD) date imputation uses both a comparison of the partial CMD start date to the treatment start date, and the value of the CMDTYP1C flag (1, 2, or 3). Event date comparisons to treatment start date are made based on the year and month values only (any day values are ignored) in [Table 5.1-3](#) below.

1. If the CMD start date year value is missing, the date will be imputed based on the CMDTYP1C flag value. If the flag value is 1 or 3, the imputed CMD start date is set to one day before the treatment start date. Else, if the flag value is missing or 2, the imputed CMD start date is set to one day after the treatment start date. (Note that for some legacy data, the CMDTYP1C variable may not exist in the data. When this happens and the CMD start date year value is missing, the imputed date value will be NULL.)
2. If the CMD start date year value is less than the treatment start date year value, the CMD started before treatment. Therefore:
  - a. if the CMD year is less than the treatment year and the CMD month is missing, the imputed CMD start date is set to the mid-year point (01JulYYYY).
  - b. Else if the CMD year is less than the treatment year and the CMD month is not missing, the imputed CMD start date is set to the mid-month point (15MONYYYY).

If the CMD start date year value is greater than the treatment start date year value, the CMD started after treatment. Therefore:

- a. If the CMD year is greater than the treatment year and the CMD month is missing, the imputed CMD start date is set to the year start point (01JanYYYY).
  - b. Else if the CMD year is greater than the treatment year and the CMD month is not missing, the imputed CMD start date is set to the month start point (01MONYYYY).
3. If the CMD start date year value is equal to the treatment start date year value:
    - a. and the CMD month is missing or the CMD month is equal to the treatment start month,
      - i. If the flag value is 1 or 3, the imputed CMD start date is set to one day before the treatment start date.
      - ii. Else, if the flag value is missing or 2, the imputed CMD start date is set to one day after the treatment start date.
    - a. Else if the CMD month is less than the treatment start month, the imputed CMD start date is set to the mid-month point (15MONYYYY).
    - b. Else if the CMD month is greater than the treatment start month, the imputed CMD start date is set to the start month point (01MONYYYY).

**Table 5.1-3: CMD date imputation**

|              | MON MISSING            | MON < CFM              | MON = CFM              | MON > CFM              |
|--------------|------------------------|------------------------|------------------------|------------------------|
| YYYY MISSING | (F)                    | (F)                    | (F)                    | (F)                    |
|              | Uncertain              | Uncertain              | Uncertain              | Uncertain              |
| YYYY < CFY   | (D)=01JULYYYY          | (C)=15MONYY            | (C)=15MONYY            | (C)=15MONYY            |
|              | Before Treatment Start | Before Treatment Start | Before Treatment Start | Before Treatment Start |

|                        |  |  |                       |                       |
|------------------------|--|--|-----------------------|-----------------------|
| YYYY = CFY      | (B)   | (C)=15MONYY   | (B)            | (A)=01MONYYYY  |
|                        | Uncertain  | Before Treatment Start   | Uncertain             | After Treatment Start |
| YYYY > CFY   | (E)= 01JANYYYY  | (A)=01MONYYYY   | (A)=01MONYYYY  | (A)=01MONYYYY  |
|                        | After Treatment Start  | After Treatment Start  | After Treatment Start | After Treatment Start |
| Before Treatment Start |  | Partial indicates date prior to Treatment Start Date                   |                       |                       |
| After Treatment Start  |  | Partial indicates date after Treatment Start Date                      |                       |                       |
| Uncertain              |  | Partial insufficient to determine relationship to Treatment Start Date |                       |                       |
| LEGEND:         |  |  |                       |                       |
| (A)             | MAX(01MONYYYY,TRTSTD+1)  |  |                       |                       |
| (B)             | IF CMDTYP1C IN (1,3) THEN TRTSTD-1
ELSE IF CMDTYP1C in( . , 2) THEN TRTSTD+1  |  |                       |                       |
| (C)             | 15MONYYYY  |  |                       |                       |
| (D)             | 01JULYYYY  |  |                       |                       |
| (E)             | 01JANYYYY  |  |                       |                       |
| (F)             | IF CMDTYP1C IN (1,3) THEN TRTSTD-1
ELSE IF CMDTYP1C in ( . , 2) THEN TRTSTD+1 |  |                       |                       |

### 5.1.3.1 Prior therapies date imputation

Not applicable.

### 5.1.3.2 Post therapies date imputation

Not applicable.

### 5.1.3.3 Other imputations

Not applicable.

## 5.2 AEs coding/grading

The verbatim term recorded on CRF will be identified as adverse event and will be coded by primary system organ class and preferred term using Medical Dictionary for Regulatory Activities (MedDRA) version 18.1 and above.

## 5.3 Laboratory parameters derivations

**Table 5.3.1 Definition of notable/extended ranges for laboratory test**

| Laboratory test                          | Criteria for notable ranges  |
|--|--|
| Platelet count                           | < 100 x 10  /L (extended range <50×10  /L)   |
| Absolute neutrophils                     | < 1.5 x 10  /L (extended range <0.5×10  /L)  |
| Serum creatinine                         | > 33% increase from baseline and > ULN at two consecutive measurements at least 7 days apart   |
| Creatinine clearance*                    | <60 mL/min at two consecutive measurements at least 7 days apart (extended range <40 mL/min at two consecutive measurements at least 7 days apart) |
| Urinary protein/urinary creatinine ratio | ≥ 1.0 (mg/mg) at two consecutive measurements at least 7 days apart  |
| ALT and AST                              | >5 x ULN and >2 x baseline value (extended range >10×ULN and >2×baseline value)  |

\* Creatinine clearance will be estimated using the Schwartz formula

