6.2.1.2 Elevations in serum creatinine

Serum creatinine should be monitored during the study as stated in the [Table 7-1](#) and [Table 7-2](#).

In case of a single clinically relevant increase in serum creatinine, the assessment will be repeated at the next visit, or as clinically indicated.

Deferasirox dose reduction by 10 mg/kg/day for the DT formulation and by 7 mg/kg/day for the FCT formulation should be performed if there is a rise in serum creatinine by 33% above baseline value resulting in a serum creatinine above the ULN on two consecutive visits (a minimum of 7 days apart).

If after a dose reduction, a progressive increase in serum creatinine beyond the ULN is observed, a treatment interruption is recommended.

After a treatment interruption, if serum creatinine falls below the age appropriate upper limit of normal range on two consecutive visits, it is recommended to resume therapy at 50% of the last dose, and after 1 month, if the serum creatinine increase does not recur, study medication can be returned to 100% of the last dose (including body weight adjustment if required).

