6.2.1.4 Changes in urine protein/creatinine ratio

Proteinuria should be monitored during the study as stated in [Table 7-1](#) and [Table 7-2](#).

In case of a single increase of the urinary protein/creatinine ratio the assessment should be repeated at the next visit.

Deferasirox dose reduction by 50% should be performed if the urinary protein/creatinine ratio increases to > 0.5 mg/mg in two consecutive second-void urine samples (a minimum of 48h apart), if all other causes of proteinuria have been excluded.

Deferasirox must be temporarily interrupted if the urinary protein/creatinine ratio increases to > 1.0 mg/mg in two consecutive second-void urine samples (a minimum of 48h apart).

Should proteinuria persist, study treatment may be discontinued if the investigator believes it is in the best interest of the patient. Novartis may be contacted by the investigator to discuss dosing options if the investigator so desires.

Dose adjustment will be based on local laboratory results.

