- Classification to compare baseline to the worst on-treatment value. Apart from the above laboratories summaries, summaries of Hepatitis Viral tests will also be performed.

In addition, a summary of serum ferritin will be presented by TDT and NTDT patients, by age group, and ICT-naive vs. ICT patients by visit.

For all lab assessments, the baseline of each period will be considered based on the actual baseline or start of that particular period, as applicable. Also the baseline data for FCT phase will be provided for only the number of patients available in the analysis set at the start of the period.

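### The urine protein/creatinine flag does not match the protocol's own confirmation rule, and the plan does not settle which baseline the creatinine and ALT/AST flags use in the FCT period.

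*SAP*

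**What the plan says.** **UPCR flag.** SAP Table 5.3.1 and Protocol Table 10-1 carry the same criterion: "≥ 1.0 (mg/mg) at two consecutive measurements at least 7 days apart". It has no lower category and no baseline term.

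**UPCR action rules.** Under Protocol 6.2.1.4, the dose is halved when the ratio "increases to > 0.5 mg/mg in two consecutive second-void urine samples (a minimum of 48h apart", provided other causes of proteinuria have been excluded. Drug "must be temporarily interrupted if the urinary protein/creatinine ratio increases to > 1.0 mg/mg in two consecutive second-void urine samples", again with a 48 h minimum. After a single raised value, "the assessment should be repeated at the next visit". SAP 5.5, deviation S13 (failure to interrupt), uses the same cut-off of above 1.0 and the same 48 h minimum.

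**Creatinine and ALT/AST flags.** Table 5.3.1 flags creatinine more than 33% above baseline and above ULN, twice, at least 7 days apart. It flags ALT/AST above 5 x ULN and above twice baseline, with an extended range above 10 x ULN and above twice baseline.

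**Baseline.** SAP 2.1.1 defines baseline as the last value before study treatment, taken on Day 1. SAP 2.8.3 says that for all laboratory assessments "the baseline of each period will be considered based on the actual baseline or start of that particular period", as applicable. Table 5.3.1 does not say which of the two it uses.

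**Extra samples.** Unless otherwise specified, SAP 2.1 averages additional or unscheduled values into the dedicated visit.

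**The concern.** Laboratory changes on FCT compared with DT are part of the secondary safety endpoint, and the notable ranges are the plan's trial-specific laboratory criteria. Two things can make them disagree with the rest of the plan.

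- A patient can meet the protocol's rule for confirmed proteinuria, and even be recorded as deviation S13 for not being interrupted, without having a notable UPCR.
- Every patient takes DT before FCT. If the FCT period is measured from Week 24, the reference is a value taken after 24 weeks on the same active substance. A rise that began on DT then becomes part of the FCT reference, and the same absolute value may be notable in one period and not in the other.

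**Working it through.** The plan states no figure to reproduce here. The check sets each flag beside its action rule and applies both to example values. All patient values below are assumed.

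**1. UPCR (mg/mg)**

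| Two consecutive values | Gap | Protocol 6.2.1.4 | Table 5.3.1 flag |
|---|---|---|---|
| 0.8, 0.8 | 4 weeks | reduction | no |
| 1.4, 1.3 | 48 h or 96 h | interruption | no |
| 1.4, 1.3 | 7 days | interruption | yes |
| 1.4, 0.9 | 7 days | reduction | no |
| 1.0, 1.0 | 7 days | reduction only | yes |

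The reduction entries assume that other causes have been excluded. Cut-off and interval both differ. In the second row, a later value of 1.0 or more could still produce a flag. If the ratio has recovered by the next visit, for example to 0.4, none arises.

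Averaging adds to this. Values of 1.3 and 1.4 taken three days apart may be presented as one visit value, (1.3 + 1.4)/2 = 1.35. No confirming reading is then left, whatever interval the flag uses.

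**2. How often the 7-day interval can matter.** The default repeat is at the next visit. Under the SAP 2.1.1 windows, the closest in-window treatment visits are Visit 3 at day 16 and Visit 4 at day 26, which are 10 days apart. A repeat at the next in-window visit therefore satisfies 7 days. The gap matters only for an earlier, extra repeat. The missing category between 0.5 and 1.0 matters at any spacing.

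**3. Creatinine: cut-off and timing.** Protocol 6.2.1.2 acts on a "rise in serum creatinine by 33% above baseline value resulting in a serum creatinine above the ULN on two consecutive visits", at least 7 days apart. With a common baseline this coincides with the flag, except at exactly 33%. Only the baseline is open.

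**4. Creatinine: effect of the baseline.** In units of ULN, the flag threshold is max(1, 1.33 x baseline). The baseline limb governs only above 1/1.33 = 0.752 x ULN. For Day 1 = 0.80 x ULN, the Day 1 threshold is 1.33 x 0.80 = 1.064, or +33%. With a Week 24 reference:

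| Change on DT | Week 24 (x ULN) | FCT threshold (x ULN) | As rise over Day 1 |
|---|---|---|---|
| -10% | 0.72 | 1.000 | +25% |
| 0 | 0.80 | 1.064 | +33% |
| +10% | 0.88 | 1.170 | +46% |
| +20% | 0.96 | 1.277 | +60% |
| +30% | 1.04 | 1.383 | +73% |

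If Day 1 and Week 24 are both at or below 0.752 x ULN, the ULN limb governs and the reset changes nothing.

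Example with ULN 0.90 mg/dL: Day 1 is 0.60, Week 24 is 0.78, and two FCT values at least 7 days apart are 0.95 and 0.96.
- From Day 1 they are +58% and +60% (0.95/0.60 = 1.58; 0.96/0.60 = 1.60). The threshold is max(0.90, 1.33 x 0.60 = 0.80) = 0.90, or +50%. Flagged.
- From Week 24 they are +22% and +23% (0.95/0.78 = 1.22; 0.96/0.78 = 1.23). The threshold is 1.33 x 0.78 = 1.04, or +73% over Day 1. Not flagged.

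Reverse example: Day 1 is 0.95, Week 24 is 0.80 and FCT is 1.10 x ULN. That is +15.8% from Day 1 and +37.5% from Week 24, so the patient is flagged only with the period-start baseline.

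**5. ALT/AST.** The threshold is max(5, 2 x baseline) in units of ULN. The baseline matters only above 5/2 = 2.5 x ULN (above 5 x ULN for the extended range). Baselines of 3 and 4 x ULN give thresholds of 6 and 8 x ULN. With Week 24 at 6 x ULN the threshold is 12, so 9 x ULN on FCT is not flagged. From a Day 1 value of 2.5 x ULN or less, it would be. Protocol 6.2.1.6 gives a qualitative action rule, a persistent and progressive rise, so there is no numeric cut-off for the flag to contradict.

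**The case against.** A reporting flag need not equal a dosing trigger, and the two tables of notable ranges agree with each other. The default UPCR repeat satisfies the 7-day interval, so the missed case above 1.0 needs an early extra repeat followed by recovery. The documents give no frequency for that. All of this stands, but it does not explain why confirmed values between 0.5 and 1.0 have no category, or why S13 and Table 5.3.1 confirm at different intervals.

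A reader might infer that renal events are hidden. The documents do not support that. Under Protocol 8.1.2.1, a laboratory abnormality needing a protocol-required dose hold is an adverse event by definition. SAP 2.8.1 tabulates adverse events leading to dose adjustment or interruption, and SAP 2.4.1 summarises dose changes with reasons. SAP 2.8.3 also plans shift tables and worst CTCAE grade regardless of baseline, the latter for hematology and biochemistry tests. It cites Table 5.3.1 only for flagging reported data. Neither document specifies a comparison of notable counts between FCT and DT.

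A reader might also infer that the flags favour FCT throughout. That is conditional: it needs a period-start baseline, a rise on DT, and a Week 24 value above the limits in the working. It reverses after a fall and cannot apply to UPCR.

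Finally, a Day 1 reference has its own weakness, because it charges FCT with rises that began on DT. That is a reason to show both references.

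**Conclusion.** The point holds for the laboratory flags only. The UPCR flag differs from Protocol 6.2.1.4 and S13 in cut-off and confirmation interval, and the averaging rule may remove the confirming sample. Which clinical threshold is right is for the sponsor to reconcile. It would be wrong to extend the mismatch to all three tests: creatinine cut-off and timing already match 6.2.1.2, and ALT/AST has no numeric action rule.

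For creatinine and ALT/AST, the defect is an unsettled baseline. If the period start applies, and if that means the Week 24 value, a rise of 10%, 20% or 30% on DT moves the FCT creatinine threshold to +46%, +60% or +73% over Day 1, once Week 24 exceeds about 0.75 x ULN. Against these, the Day 1 reference requires +33%, or more where the ULN limb governs. For ALT/AST the limit is 2.5 x ULN at Week 24. The number of patients affected cannot be derived from the documents. The correction is inexpensive and worth making before the final analysis.

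**What to change.** Change reporting only; no dosing rule is altered.

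1. In SAP Table 5.3.1, reconcile the UPCR row with Protocol 6.2.1.4 and S13 by reporting confirmed above-0.5 and above-1.0 categories at the protocol's confirmation interval. Protocol Table 10-1 carries the same row, so note the change in SAP Section 4, which now lists none.
2. State that repeat samples are kept as separate measurements when confirmation is assessed, as an exception to the averaging rule in SAP 2.1.
3. Show the creatinine and ALT/AST flags against Day 1 in both periods, beside the period-start version. Split the FCT-period flags into those new on FCT and those already met on DT.

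The cost is SAP wording and programming on data already collected, somewhat more flagged patients, and one extra table split. Item 2 assumes that unscheduled repeats are in the database with their dates.

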5.2 Inclusion criteria

Patients eligible for inclusion in this study have to meet **all** of the following criteria:

1. Prior to any screening procedures being performed, written informed consent/assent must be provided. For pediatric patients, consent will be obtained from the parent(s) or the patient's legal representative. Investigators will also obtain assent of patients according to local, regional or national guidelines.
2. Male and female patients aged ≥ 2 years
3. Deferasirox naïve patient or a chelation naïve patient or a patient treated by other chelators for at least 6 months continuously, such as:
 - a. Deferiprone (DFP)
 - b. Deferoxamine (DFO)
 - c. Combination (DFO + DFP)
4. Subject is willing to discontinue current iron chelation therapy at least 5 days prior to the Study day 1 and for the duration of the study
5. Patients with transfusion-dependent thalassemia (independent of underlying condition) with transfusional iron overload as shown by:
 - a serum ferritin level of > 1000 ng/ml at screening and if available, LIC > 3 mg Fe/g dw within 6 months prior to screening
6. Patients with non-transfusion-dependent thalassemia with iron overload as shown by:
 - a serum ferritin level of ≥ 800 ng/ml at screening and if available, LIC ≥ 5 mg Fe/g dw within 6 months prior to screening

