7.2.2.6.2 Clinical chemistry

Clinical chemistry samples will be collected as described in [Table 7-1](#) and [Table 7-2](#) following local standard practice.

Parameters to be measured will include: albumin, alkaline phosphatase, ALT (SGPT), AST (SGOT), bicarbonate, calcium, chloride, serum creatinine, creatine kinase, glucose, inorganic phosphorus, potassium, sodium, total bilirubin (direct and indirect bilirubin only required if total bilirubin is > 1.5 ULN) total cholesterol, LDL, HDL, lactate dehydrogenase (LDH), total protein, triglycerides, blood urea nitrogen (BUN) or urea, uric acid, C-reactive protein (CRP).

In addition, serum creatinine will be measured every 2 weeks during the first four weeks after first study drug administration and then monthly. Refer to [Table 7-1](#) and [Table 7-2](#) for specifics.

Creatinine clearance will be estimated using the Cockcroft-Gault equation for adult patients and Schwartz formula for pediatric patients. This estimate will be provided each time serum creatinine is collected. The formula should be consistently used throughout the study for a particular patient.

Use the following reference source for calculation of creatinine clearance:

- <https://reference.medscape.com/calculator/creatinine-clearance-cockcroft-gault>
- <http://wwwusers.med.cornell.edu/~spon/picu/calc/crclsch2.htm>

Serum ferritin test will also be performed at the screening visit to assess the eligibility of the patient. Serum ferritin testing will also be performed as described on [Table 7-1](#) and [Table 7-2](#).

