### 2.2.1 Subgroup of interest

Since this study also includes pediatric patients, all key safety and efficacy analyses will be performed separately by age groups: 2-6 years (infant), 7-11 years (child), 12-17 years (adolescent), < 18 years (overall of infant, child and adolescent), and  $\geq$  18 years (adult). In addition, these summaries will be performed on prior intake of iron chelation status (naïve or pre-treated) and thalassemia transfusion status (TDT or NTDT).

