## 2.8.3 Laboratory data

The summary of laboratory evaluations will be presented for different groups of laboratory tests (hematology, serum chemistry, serum ferritin, serum creatinine, and urinalysis) for different treatment periods (core and extension). Descriptive summary statistics for the change from baseline to each study visit will be presented. These descriptive summaries will be presented by test group, laboratory test and treatment group. Change from baseline will be summarized only for the patients who have both baseline and post-baseline assessment. For each parameter, maximum change from baseline within each study period will be evaluated analogously.

In addition, shift tables will be provided for all parameters to compare a patient's baseline laboratory evaluation relative to the visit's observed value. For the shift tables, the normal laboratory ranges will be used to evaluate whether a particular laboratory test value was normal, low, or high for each visit value relative to whether or not the baseline value was normal, low, or high. These summaries will be presented by laboratory test and treatment group. Shifts will be presented by visit as well as for most extreme values post-baseline.

Grading of laboratory values will be assigned programmatically as per NCI Common Terminology Criteria for Adverse Events (CTCAE). The calculation of CTCAE grades will be based on the observed laboratory values only, clinical assessments will not be taken into account.

CTCAE Grade 0 will be assigned for all non-missing values not graded as 1 or higher. Grade 5 will not be used.

For laboratory tests where grades are not defined by CTCAE, results will be categorized as low/normal/high based on laboratory normal ranges.

The following summaries will be generated separately for hematology and biochemistry tests:

- Reporting of all laboratory data with values flagged to show the corresponding CTCAE grades if applicable and the classifications relative to the laboratory normal ranges ([Table 5.3.1](#))

For laboratory tests where grades are defined by CTCAE

- Worst post-baseline CTCAE grade (regardless of the baseline status). Each patient will be counted only once for the worst grade observed post-baseline.
- Shift tables using CTCAE v4.3 grades to compare baseline to the worst on-treatment value

For laboratory tests where grades are not defined by CTCAE

- Shift tables using the low/normal/high/ (low and high)

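### The footnotes behind the creatinine-clearance flags name only the Schwartz formula, while protocol 7.2.2.6.2 assigns Cockcroft-Gault to adults, so adults can be misclassified in either direction

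*SAP*

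**What the plan says.** Protocol 7.2.2.6.2 (Clinical chemistry) sets the formula by age: "Creatinine clearance will be estimated using the Cockcroft-Gault equation for adult patients and Schwartz formula for pediatric patients". It adds: "The formula should be consistently used throughout the study for a particular patient". The same section says that the estimate accompanies every serum creatinine result, and protocol Tables 7-1 and 7-2 list creatinine clearance as a database item at each visit through Week 96.

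SAP Table 5.3.1 defines the notable range for clearance as "<60 mL/min at two consecutive measurements at least 7 days apart (extended range <40 mL/min at two consecutive measurements at least 7 days apart". An asterisk on that row leads to the footnote "Creatinine clearance will be estimated using the Schwartz formula". Protocol Table 10-1 (section 10.5.3.3) carries the same criteria and the same footnote. Neither footnote mentions age.

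The population is "Male and female patients aged ≥ 2 years", with no upper limit, and SAP 2.2.1 defines an adult group from 18 years. SAP 2.8.3 cites Table 5.3.1 in one place: "Reporting of all laboratory data with values flagged to show the corresponding CTCAE grades if applicable and the classifications relative to the laboratory normal ranges". SAP section 4 declares no change to protocol-specified analyses.

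**The concern.** The two instructions cannot both be met for an adult. A programmer who follows the table footnote would compute a height-based Schwartz value for a 40-year-old, while the database holds a Cockcroft-Gault value for the same blood sample. The two formulas use different patient characteristics (height in one; age, weight and sex in the other), so they can fall on opposite sides of 60 or 40 mL/min.

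Renal laboratory values matter in this trial. Comparing the two formulations on laboratory values is a stated safety objective (protocol Table 3-1). Protocol 1.2.1.2 discusses whether the higher peak concentration of the newer formulations could worsen renal values. A clearance flag that depends on which sentence the programmer read is a weak basis for that comparison.

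**Working it through.** **Setting the passages side by side**

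- Protocol 7.2.2.6.2: Cockcroft-Gault for adults, Schwartz for children, one formula per patient.
- Protocol Table 10-1 footnote: Schwartz, no age limit.
- SAP Table 5.3.1 footnote: Schwartz, no age limit.
- SAP section 1: algorithms follow the protocol unless otherwise specified. This does not settle the matter, because the protocol says both things.

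The protocol therefore contradicts itself, and the SAP carries the conflict forward.

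**Does the choice change the flag?** The plan gives no figure to reproduce and does not print either formula; the protocol only points to calculators ("Use the following reference source for calculation of creatinine clearance"). The forms and constants below are therefore assumptions:

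- Cockcroft-Gault = (140 − age) × weight / (72 × SCr), times 0.85 for women.
- Schwartz = k × height / SCr, tried at k = 0.413, 0.55 and 0.70.

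Units are years, kg, cm and mg/dL. The flag needs two low values in a row, a week or more apart, so each creatinine below is taken to hold at both measurements.

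Woman, 40 years, 45 kg, 155 cm, SCr 1.0:
- Cockcroft-Gault = 100 × 45 × 0.85 / 72 = 53.1
- Schwartz = k × 155 = 64.0, 85.3, 108.5

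Man, 20 years, 60 kg, 165 cm, SCr 1.6:
- Cockcroft-Gault = 120 × 60 / (72 × 1.6) = 62.5
- Schwartz = k × 165 / 1.6 = 42.6, 56.7, 72.2

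| Assumed adult | Cockcroft-Gault | Schwartz, k = 0.413 | k = 0.55 | k = 0.70 |
|---|---|---|---|---|
| Woman of 40 | 53.1, flagged | 64.0, not flagged | 85.3, not flagged | 108.5, not flagged |
| Man of 20 | 62.5, not flagged | 42.6, flagged | 56.7, flagged | 72.2, not flagged |

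**Width of the disagreement for the woman of 40.** Cockcroft-Gault reaches 60 at SCr = 53.1 / 60 = 0.89. Schwartz reaches 60 at SCr = 64.0 / 60 = 1.07, 85.3 / 60 = 1.42 or 108.5 / 60 = 1.81. Any sustained creatinine between 0.89 and that upper value is flagged by one formula and missed by the other.

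**Direction in general.** The ratio Schwartz / Cockcroft-Gault = 72 × k × height / [(140 − age) × weight × (0.85 if female)] does not depend on creatinine. For ages 18 to 60 and body sizes from 40 kg/150 cm to 75 kg/175 cm it runs:

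- k = 0.413: 0.57 to 1.64
- k = 0.55: 0.76 to 2.18
- k = 0.70: 0.96 to 2.78

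Over a wider uniform grid (18 to 65 years, 35 to 85 kg, 140 to 185 cm, both sexes), Schwartz reads higher in 40%, 71% and 91% of cells respectively. The grid is an assumption and does not represent the trial population. It shows that the disagreement runs both ways and that its balance depends on k.

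**The case against.** The strongest reply is that little may go wrong in practice. The footnote names no population, and clearance is already recorded at every visit under the age-specific rule. A programmer could simply flag the recorded values, with adults already on Cockcroft-Gault. That is possible, so it is not established that adult flags will be computed by Schwartz. But the footnote as written tells the programmer to do so, and nothing in the SAP overrides it.

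A second reply is that the same table has criteria for serum creatinine and urine protein/creatinine ratio that need no formula. These give adults some cover. They are not equivalent: the creatinine criterion needs both a rise of more than 33% from baseline and a value above the upper limit of normal, so it can miss low clearance with creatinine inside the normal range.

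Three stronger readings are tempting and are not supported:

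- A reader might infer that the SAP departs from the protocol. Protocol Table 10-1 has the same footnote.
- A reader might infer that dosing or eligibility is affected. The on-treatment renal dose rules in protocol 6.2.1.2 and 6.2.1.4 use serum creatinine and urine protein/creatinine ratio. Exclusion criterion 1 refers to a limit in local prescribing information, not to this table.
- A reader might infer that the error only hides low clearance. The man of 20 above shows the reverse.

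**Conclusion.** The conflict among protocol 7.2.2.6.2, protocol Table 10-1 and SAP Table 5.3.1 is real and undeclared. If the footnote is followed, some adults are misclassified in the laboratory flags, including sustained low clearance left unflagged. The gap can be large for one patient (53 against 64 to 109 mL/min in the example). How many trial patients are affected cannot be stated: the documents give neither the formula constants nor the adults' body sizes and creatinine values.

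The reach is limited. The only use of Table 5.3.1 that the SAP shows is flagging in laboratory reporting, which protocol 10.5.3.3 calls a listing. The groups that SAP 2.8.3 names for summary do not include creatinine clearance. A reader might expect every safety table to be affected; the documents do not show that. The primary endpoint, its error rate and its power are untouched. This is an inexpensive correction worth making, not a threat to the trial's main conclusion.

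**What to change.** Reconcile both footnotes with protocol 7.2.2.6.2. Suggested wording for protocol Table 10-1 and SAP Table 5.3.1: clearance is estimated by Cockcroft-Gault for adult patients (18 years and older, as in SAP 2.2.1) and by Schwartz for pediatric patients; each patient stays on the formula used at baseline, including a patient who turns 18 on study. The last clause is needed because treatment can run to 96 weeks and 7.2.2.6.2 asks for one formula per patient. Also state the Schwartz constant, since the flag depends on it. If Schwartz for adults was intended, record it with a reason in SAP section 4 instead.

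The cost is two footnotes and a short change to the derivation code. Age, sex, weight at every visit, height at screening and Week 48, and serum creatinine at every visit are already collected. SAP 2.14 places key safety analyses of the core phase at the Week 48 interim, so if those flags used Schwartz for adults they should be rerun and the change noted in the SAP's document history.
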